6 STUDY PARAMETERS

6.1 Efficacy Measures

The hierarchical primary efficacy variables are the following:

- 1. Absence of anterior chamber cells (i.e., score of '0') at Visit 5 (Day 15) for:
 - a. The 1.0% concentration of RTA 408 Ophthalmic Suspension compared to Placebo
 - b. The 0.5% concentration of RTA 408 Ophthalmic Suspension compared to Placebo.
- 2. Absence of pain (i.e., score of '0') at Visit 3 (Day 4) for:
 - a. The 1.0% concentration of RTA 408 Ophthalmic Suspension compared to Placebo; to be tested if 1a. is statistically significant in favor of the active arm.
 - b. The 0.5% concentration of RTA 408 Ophthalmic Suspension compared to Placebo; to be tested if 1b. is statistically significant in favor of the active arm.
 - 6.1.1 Secondary Efficacy Variables
 - 1. Absence of anterior chamber cells at Visits 3, 4, or 6 (Days 4±1, 8±1, or 21±1, respectively)
 - 2. Absence of pain at Visits 4, 5 or 6 (Days 8 ± 1 , 15+1 or 21 ± 1 , respectively)
 - 3. Absence of flare at Visits 3, 4, 5 or 6 (Days 4 ± 1 , 8 ± 1 , 15 ± 1 or 21 ± 1 , respectively)

6.2 Safety Measures

- Slit lamp biomicroscopy
- Pin-hole visual acuity
- IOP
- Dilated indirect ophthalmoscopic examination
- AE monitoring

6.3 Other Measures

None.

7 STUDY MATERIALS

7.1 Study Treatments

7.1.1 Study Treatments/Formulations

The drug product is a sterile aqueous suspension he concentrations to be tested are the following:

- RTA 408 Ophthalmic Suspension 0.5%
- RTA 408 Ophthalmic Suspension 1.0%
- Placebo for RTA 408 Ophthalmic Suspension

7.1.2 Instructions for Use and Administration

- Twenty-four ± 6 hours after surgery (Day 1), a trained technician will instruct patients on how to instill the study drug. The first dose will be instilled in-office at the patient's Day 1 visit.
- •
- Instructions to patients on study drug administration will include: SHAKE WELL BEFORE USE. Instill one drop twice daily for 14 days in the morning and evening (approximately 12 hours apart) in the eye that underwent surgery. Study drugmust not be instilled within 30 minutes of instillation of any other ocular medications or artificial tears

Discontinue use of the study drug after instilling the second dose on Day 14. Keep out of reach of children.

• All bottles of active and placebo treatment will be identical in appearance and will be packaged in identical containers. The study drug kit and each bottle will have a label bearing information on each part. Study drug will be packaged and labeled based on the randomization list generated prior to the start of the study.

7.2 Other Study Supplies

Urine pregnancy tests [Clarity HCG tests] will be supplied.

8 STUDY METHODS AND PROCEDURES

8.1 Patient Entry Procedures

8.1.1 Overview

Patients as defined by the criteria in section 5.2, 5.3, and 5.4 will be considered for entry into this study. See Appendix 2 for a tabular summary of study visits and procedures required for each visit.

8.1.2 Informed Consent

Prior to a patient's participation in the trial (i.e., changes in a patient's medical treatment and/or study related procedures), the study will be discussed with each patient, and patients wishing to participate must give written informed consent using an informed consent form. The informed consent form must be the most recent version that has received approval/favorable review by a properly constituted Institutional Review Board.

8.1.3 Washout Intervals

Study staff will confirm that the patient has not used prior to Day 1 for the indicated washout interval, any of the following disallowed medications, systemically or in the study eye, grouped by washout period:

72 hours

• Contact lens or a collagen shield in the study eye

7 days

- Topical ocular corticosteroid
- Topical ocular NSAID

14 days

- Systemic corticosteroids
- Systemic analgesics/pain relievers (e.g., gabapentin, pregabalin, NSAIDs and opioids)

Note: Use of acetaminophen (up to 4,000 mg/day) and 'baby' aspirin (up to 81 mg/day) during the study are allowed. Use of an opioid during cataract surgery is allowed.

28 days

- Periocular injection of any corticosteroid solution
- Systemic medications for BPH (tamsulosin, silodosin, alfuzosin, finasteride)

56 days

• Corticosteroid depot in the study eye (after implantation)

• Topical ocular cyclosporine

8.1.4 Procedures for Final Study Entry

Patients must satisfy all inclusion and none of the exclusion criteria in order to be entered into the study on Study Visit 2.

8.1.5 Methods for Assignment to Treatment Groups

All patients screened for the study who sign a consent form will be assigned a 3-digit screening number which will be entered in the Screening and Enrollment Log. The Patient ID number will be a 7-digit number consisting of the 4-digit site number combined with the 3-digit screening number.

Once a patient meets all qualification criteria, they will be randomly assigned to masked treatment using a 1:1:1 (0.5% RTA 408: 1.0% RTA 408: placebo) assignment ratio. Patients will be randomized on the first day post-surgery (Day 1) by assignment of the lowest 5-digit study drug kit number available at their investigative site. No study drug kit numbers will be skipped or omitted. A trained, unmasked technician will administer study drug from the bottle of the study drug kit assigned to the patient. Each study drug kit will be labeled with the 5-digit study drug kit number. The bottle of study drug will be dispensed to the patient for use on subsequent days.

8.2 **Concurrent Therapies**

The use of any concurrent medication, prescription or over-the-counter, used within the last 60 days before Visit 1 and for the duration of the study is to be recorded on the patient's source document and corresponding case report form (eCRF) along with the reason the medication was taken.

Concurrent enrollment in another investigational drug or device study is not permitted.

8.2.1 Prohibited Medications/Treatments

Prohibited medications/treatments for the duration of the study are:

- Topical ocular corticosteroid in the study eye
- Topical ocular NSAID in the study eye
- Systemic corticosteroids
- Periocular injection of any corticosteroid solution in the study eye
- Corticosteroid depot in the study eye (after implantation)
- Topical ocular cyclosporine in the study eye
- Anti-inflammatory or immunomodulating agents systemically, or in the study eye.

- Systemic medications for benign prostatic hyperplasia (BPH) (e.g., tamsulosin, silodosin, alfuzosin, finasteride).
- Systemic Analgesics/pain relievers, including opioids, narcotics and other pain medications systemically (e.g., gabapentin, pregabalin, NSAIDs and opioids).

Note: Use of acetaminophen (up to 4,000 mg/day) and 'baby' aspirin (up to 81 mg/day) during the study are allowed. Use of an opioid during cataract surgery is allowed.

- Glaucoma medications or ocular hypertension medications in the study eye
- Contact lens or a collagen shield in the study eye
- Non-diagnostic topical ophthalmic solutions (other than perioperative mydriatics, anesthetics and antiseptics, prophylactic antibiotics, lid scrubs for mild blepharitis, or artificial tears for the management of dry eye) in the study eye
- Antineoplastic therapy
- Any other ophthalmic surgical procedure (e.g., vitrectomy, relaxing incisions, iridectomy, conjunctival excisions, use of iris hooks or other iris dilators, etc.) in addition to the cataract extraction procedure and PCIOL implantation in the study eye
- Plan to have laser or incisional surgery in the study eye (other than cataract surgery);
- Surgery planned or scheduled for the contralateral eye;

If a patient uses a disallowed medication, this use will be recorded as a protocol violation. Protocol violations must be reported to the IRB in accordance with their standard operating procedures.

8.2.2 Escape Medications

Use of escape medications should be avoided if possible. If in the investigator's assessment escape medication is required due to lack of efficacy, the study drug should be discontinued prior to administration of the first dose of escape medication. The patient should remain in the study, and continue to be followed per the protocol for all remaining visits and assessments to the end of the study. These patients who require escape medication should be considered as discontinued from study medication due to lack of efficacy, and the escape medication(s) used must be documented in the eCRF.

8.2.3 Special Diet or Activities

Not applicable.

8.3 Examination Procedures

8.3.1 Procedures to be Performed at Each Study Visit with Regard to Study Objectives

8.3.1.1 VISIT 1: Screening Visit (Day -1 to Day -28)

- Informed Consent/HIPAA: Prior to any changes in a patient's medical treatment and/or performing study visit procedures, the study will be discussed with each patient and patients wishing to participate must give written informed consent and sign a HIPAA form.
- Review of Inclusion and Exclusion Criteria: If patients meet all initial inclusion and none of the exclusion criteria, they may complete this visit.
- Demographic data and medical/medication/ocular history: Collect and record all demographic data, medical history, any medications (refer to Section 8.2) and any underlying condition(s). Current underlying conditions, including those that began within the last thirty days, which may have been resolved before screening must be recorded. Record any medications the patient is taking, as well as those the patient may have taken but discontinued within 60 days prior to screening (refer to Section 8.2).
- Urine Pregnancy Test (for females of childbearing potential): Women of childbearing potential must have a negative urine pregnancy test to continue in the study and must agree to use an adequate method of contraception for the duration of the study in order to be enrolled. Acceptable forms of birth control are spermicide with barrier, oral contraceptive, injectable or implantable method of contraception, transdermal contraceptive, intrauterine device, or surgical sterilization of partner.
 - For non-sexually active females, abstinence will be considered an acceptable form of birth control.
- Assessment of Ocular Pain: Patients will assess ocular pain in the study eye (see Appendix 1).
- *Pin-Hole Visual Acuity Utilizing an ETDRS Chart:* Patients must have a potential post-operative pin-hole VA < 1.0 logMAR in the operative eye and in the fellow eye as measured using an ETDRS chart.
- Slit Lamp Biomicroscopy: A slit lamp exam will be performed in both eyes to exclude patients with disallowed ocular conditions (see Appendix 1).

- Assessment of Ocular Inflammation: The Investigator will assess anterior chamber cells and flare in the study eye using slit lamp biomicroscopy (see Appendix 1).
- Assessment of Intraocular Pressure: Tonometry will be used to assess intraocular pressure in both eyes. Patients who have ocular hypotension (IOP≤ 5mmHg) or are taking medications to treat ocular hypertension/glaucoma in the study eye will be excluded from the study.
- Dilated Indirect Ophthalmoscopic Examination: Dilated indirect ophthalmoscopic examination will be performed in both eyes for safety purposes (see Appendix 1).
- Schedule for Visit 2

8.3.1.3 VISIT 3: (Day 4±1)

- Update of Medical/Medication History
- Review of Study Drug Compliance Diary
- Assessment of Ocular Pain
- Pin-Hole Visual Acuity Utilizing an ETDRS Chart
- Slit Lamp Biomicroscopy
- Assessment of Ocular Inflammation
- Assessment of Intraocular Pressure
- AE Query
- Schedule for Visit 4

8.3.1.4 VISIT 4 (Day 8 ± 1)

- Update of Medical/Medication History
- Review of Study Drug Compliance Diary
- Assessment of Ocular Pain
- Pin-Hole Visual Acuity Utilizing an ETDRS Chart
- Slit Lamp Biomicroscopy
- Assessment of Ocular Inflammation
- Assessment of Intraocular Pressure
- AE Query
- Schedule for Visit 5

8.3.1.5 VISIT 5 (Day 15+1)

- Update of Medical/Medication History
- Review of Study Drug Compliance Diary
- Collection of Study Drug and Study Drug Compliance Diary
- Assessment of Ocular Pain
- Pin-Hole Visual Acuity Utilizing an ETDRS Chart

- Slit Lamp Biomicroscopy
- Assessment of Ocular Inflammation
- Assessment of Intraocular Pressure
- AE Query
- Schedule for Visit 6

8.3.1.6 VISIT 6/ EXIT VISIT (Day 21 ± 1 or Early Exit)

- Update of Medical/Medication History
- Review of Study Drug Compliance Diary³
- Collection of Study Drug and Study Drug Compliance Diary⁵
- Assessment of Ocular Pain
- Pin-Hole Visual Acuity Utilizing an ETDRS Chart
- Slit Lamp Biomicroscopy
- Assessment of Ocular Inflammation
- Assessment of Intraocular Pressure
- Dilated Indirect Ophthalmoscopic Examination
- AE Query
- Urine Pregnancy Test for Women of Childbearing Potential
- *Exit:* Patients will exit the study.

8.4 Schedule of Visits, Measurements and Dosing

8.4.1 Scheduled Visits

Refer to Appendix 2 for a schedule of visits and measurements.

8.4.2 Unscheduled Visits

These visits may be performed in order to ensure patient safety. All information gathered at unscheduled visits should be recorded on the Unscheduled Visit pages of the Source Document and corresponding eCRF.

If a randomized patient does not attend their scheduled visit, the eCRF pages for the missed visit will be skipped.

³ These procedures are to be completed on Visit 6 only if not performed at Visit 5.

All efforts should be made to schedule patients for an Exit Visit to complete Exit Procedures. Information from Early Exit Visits should be recorded on the Visit 6/Exit Visit pages.

Evaluations that may be conducted at an Unscheduled Visit (as appropriate, depending on the reason for the visit) include:

- Update Medical/Medication History
- Review/Collect Study Drug Compliance Diary and Study Drug
- Assessment of ocular pain
- Pin-hole visual acuity
- Slit lamp biomicroscopy
- Assessment of Ocular Inflammation
- Intraocular pressure measurement
- Dilated indirect ophthalmoscopic examination
- Assessment of AEs
- Urine pregnancy test (for females of childbearing potential)

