At Visits 3 (Day 4 ± 1), 4 (Day 8 ± 1), and 5 (Day 15 ± 1), patients' medical and medication histories will be updated, patients will be queried for ocular pain, pin-hole visual acuity will be assessed, and the Investigator will perform a slit lamp biomicroscopic evaluation, IOP measurement, and grading of anterior chamber inflammation. AEs will be noted, and the Study Drug Compliance Diary will be reviewed. Day 14 will be the last day of study drug treatment at home. On Visit 5 (Day 15 ± 1), the study drug and Study Drug Compliance Diary will be collected.

At Visit 6 (Day 21 ± 1), patients' medical and medication histories will be updated, patients will be queried for ocular pain, pin-hole visual acuity will be assessed, and the Investigator will perform a slit lamp biomicroscopic evaluation, IOP assessment, and grading of anterior chamber inflammation. A dilated indirect ophthalmoscopic examination will also be performed. AEs will be noted, and a urine pregnancy test will be given to females of childbearing potential. Patients will then exit the study.

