5.3 Inclusion Criteria

Each patient must meet the following criteria:

- 1. Have provided written informed consent, approved by the appropriate institutional review board;
- 2. Be able to comply with study requirements and visit schedule;
- 3. Be greater than or equal to 18 years of age of either sex or any race;
- 4. Have undergone unilateral cataract extraction via phacoemulsification and posterior chamber intraocular lens (PCIOL) implantation in the study eye on the day prior to study enrollment/randomization;
- 5. Have a grade of ≥ 2 in anterior chamber cell score on day after surgery (Day 1) in the study eye;

- 6. Have a potential post-operative pin-hole visual acuity (VA) < 1.0 logarithm of the minimum angle of resolution (logMAR) in the operative eye and fellow eye as measured using an Early Treatment for Diabetic Retinopathy Study (ETDRS) chart;
- 7. (For females of childbearing potential) agree to have urine pregnancy testing performed at screening (must be negative) and at exit visit; must not be lactating; and must agree to use a medically acceptable form of birth control² throughout the study duration. Women of childbearing potential include all females who have experienced menarche and have not experienced menopause (as defined by amenorrhea for greater than 12 consecutive months) or have not undergone successful surgical sterilization (hysterectomy, bilateral tubal ligation, or bilateral oophorectomy).

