6.3 Handling of Dropouts or Missing Data

The primary analyses of all efficacy data will use LOCF to impute missing data; data for visits after a patient is discontinued for lack of efficacy will be imputed as failures for success/failure endpoints and will be imputed using LOCF for other endpoints.

Statistical Analysis Plan Protocol

Version SIGNIFICANTLY D

RTA 408-C-1307 1.0

Per Protocol analyses will use observed data only, with the exception of patients who have missing data due to discontinuation of study treatment for lack of efficacy; for these patients, data after discontinuation will be imputed as failures.

To check robustness of results, sensitivity analyses of the primary efficacy data will be performed. These include analyses of observed data only, imputing data from patient visits after discontinuation for lack of efficacy as failures and analyses in which all missing data are imputed using multiple imputation methodology.

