7.1 General Study Design

This Phase 2, multi-center, double-masked, randomized, placebo-controlled, dose-ranging, study is designed to evaluate the clinical efficacy and safety of RTA 408 Ophthalmic Suspension 0.5% and RTA 408 Ophthalmic Suspension 1.0% compared to placebo in patients following ocular surgery. Approximately 105 male and female patients at least 18 years of age undergoing unilateral cataract extraction via phacoemulsification in one eye and meeting all other study eligibility criteria will be randomized to receive treatment with one of the two study drugs or placebo. Scheduled visits are to occur as follows: Visit 1 (Screening, Day ≥-28), Visit 2 (Day 1; 24 ±6 hours post-surgery), Visit 3 (Day 4 ±1 day), Visit 4 (Day 8 ±1 day), Visit 5 (Day 15 +1 day) and Visit 6 (Day 21 ±1 day; Exit Visit).

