9.2 Per Protocol

The Per Protocol (PP) population is a subset of the ITT population and includes patients who remain in the study through Visit 5 (Day 15) with no major protocol violations that would affect the assessment of the primary efficacy endpoints of the study [major protocol violations that would affect the assessment of the primary efficacy endpoints of the study will be determined and documented through a masked review of protocol violations prior to unmasking the study treatment assignments]. Patients without major protocol violations thought to affect the primary efficacy outcome who discontinue the study treatment due to lack of efficacy will be analyzed in the PP analysis with data after study treatment discontinuation imputed as failures for success/failure endpoints and will be imputed using last observation carried forward (LOCF) for the data obtained immediately prior to study medication discontinuation for other endpoints. Otherwise, this population will be analyzed as treated using observed data only for confirmatory analyses.

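### Does filing early-exit exams on the Visit 6 pages leave the Day 4 pain and Day 15 cell endpoints undefined?

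*Protocol*

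**What the plan says.** On data capture, Protocol 8.4.2 gives two instructions. For a patient who leaves early, "Information from Early Exit Visits should be recorded on the Visit 6/Exit Visit pages". For a missed visit, "If a randomized patient does not attend their scheduled visit, the eCRF pages for the missed visit will be skipped". The Visit 6 procedures in Protocol 8.3.1.6 include the pain and inflammation assessments, so an exit exam yields efficacy data.

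On analysis, SAP 3.1 defines the primary variables as absence of cells at Visit 5 (Day 15) and absence of pain at Visit 3 (Day 4). SAP 6.3 states: "The primary analyses of all efficacy data will use LOCF to impute missing data". Visits after discontinuation for lack of efficacy are scored as failures on success/failure endpoints. SAP 6.3 gives no ordering for LOCF and does not say whether the pre-dose baseline may be carried. Only SAP 9.2 ties LOCF to a point in time, "imputed using last observation carried forward (LOCF) for the data obtained immediately prior to study medication discontinuation for other endpoints", and that covers lack-of-efficacy patients in the per-protocol analysis of endpoints other than success/failure.

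SAP 7.1 gives scheduling windows, among them "Visit 5 (Day 15 +1 day) and Visit 6 (Day 21 ±1 day; Exit Visit". No section sets separate analysis windows or assigns exit exams to visits.

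**The concern.** A label-based derivation and a date-based one can give different answers for the same eye. Suppose a patient leaves on Day 11 for an adverse event, with grade 1 cells at Visit 4 and no cells at exit. By date, the exit exam is carried to Day 15 and the eye is a success. By visit number, the exit exam is Visit 6, after Visit 5, so Visit 4 is carried and the eye is a failure.

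Pain looks worse. No post-dose visit precedes Visit 3, so if the exit exam is passed over, the only earlier on-study score is the pre-dose one from Visit 2. Entry requires inflammation ("Have a grade of ≥ 2 in anterior chamber cell score on day after surgery (Day 1) in the study eye") but sets no minimum pain on Day 1. A carried baseline cell grade is therefore always a failure, but a carried baseline pain score can be a success. A patient who was pain-free on Day 1 and left on Day 3 in pain could be counted as pain-free on Day 4.

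The observed-data and missing-as-failure tables raise a related question. They use no LOCF for these patients, so an in-window exam left under Visit 6 would make an examined eye missing or a failure.

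**Working it through.** **Inputs.** 35 enrolled per arm to complete 31 (Protocol 5.1). Visit 3 is Day 4 ±1 and Visit 4 is Day 8 ±1 (SAP 7.1). Visit 5 runs to Day 16 under either printed window. The test is one-sided at 0.10 (SAP 5). The documents give no rate of early exit with an exit exam, and the sample-size text is not visible in the public copy, so there is no stated figure to reproduce.

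**Step 1: which exit exams are passed over under each reading.** The days considered are those before or within the target window and, for cells, after the latest Visit 4 day (Day 9).

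| LOCF reading | Pain, exits Days 2–5 | Cells, exits Days 10–16 |
|---|---|---|
| By visit number | 4 of 4 days | 7 of 7 days |
| By date, stopping at Day 4 or Day 15 | 1 of 4 (Day 5) | 1 of 7 (Day 16) |
| By date, through the visit window | 0 of 4 | 0 of 7 |

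The first row requires an order that the SAP does not state and that departs from the ordinary meaning of a last observation. Filing on the Visit 6 pages is a data-entry instruction and does not set the order. The second row requires a cutoff at the nominal day. No section sets one: the endpoints are at visits, and those visits have windows. The third row is the natural reading, and nothing is lost under it. The baseline-carry question also disappears there for any eye with an exit exam.

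**Step 2: the tables without LOCF.** Protocol 8.4.2 skips a visit's pages only when the patient does not attend. A patient examined on Day 4 or Day 15 has attended Visit 3 or Visit 5, so nothing tells the site to leave those pages blank. If a site did so for one successful eye, 12/35 = 34.3% would become 11/34 = 32.4% in observed data and 11/35 = 31.4% with missing as failure. The per-protocol pain result is not exposed: SAP 9.2 requires patients to stay through Visit 5 unless they stop for lack of efficacy, so other exits on Days 3 to 5 are outside that population.

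**Step 3: size.** One eye is 1/35 = 2.9 points. The allowance is 35 − 31 = 4 per arm for all losses to Day 21. It is a planning figure, not a cap, but it includes lack-of-efficacy exits, patients with no exit exam and exits after Day 16. As an extreme assumption, let all 4 be relevant, half of them differ in zero/non-zero status, and exit days be spread evenly:

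- Pain, date order with the nominal-day stop: 4 × 0.5 × 1/4 = 0.5 eyes; 0.5/35 = 1.4 points.
- Cells, same rule: 4 × 0.5 × 1/7 = 0.29 eyes; 0.29/35 = 0.8 points.
- Date order through the window: 0 eyes for both.

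**Step 4: could one eye matter?** With p = (a + b)/70 and z = [(a − b)/35] / √[p(1 − p) × 2/35], illustrative counts of 12 versus 7 responders give one-sided P = 0.090, and 11 versus 7 give 0.137. One eye crosses 0.10 only when the result is already borderline.

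**Step 5: the Visit 5 window.** Protocol 4 has "On Visit 5 (Day 15 ± 1), the study drug and Study Drug Compliance Diary will be collected"; Protocol 8.3.1.5 has "VISIT 5 (Day 15+1", as do the Synopsis and SAP 7.1. The Appendix 2 footnote reads ±1, and Protocol 6.1.1 shows both forms. For LOCF by date this does not matter: a Day 14 exit exam is either the Visit 5 value or the value carried to Visit 5, and so the same score. It could matter only for a Day 14 exit in the tables without LOCF.

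**The case for a change.** The strongest case for a change is that the rule would cost two sentences, while SAP 8 places the analyses after treatment codes are unmasked, so an unwritten choice could be made with results in view. The filing instruction also sits under the protocol's heading for unscheduled visits, and SAP 6.4 generally keeps unscheduled data out of the summary tables, so a programmer might exclude exit exams altogether.

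Part of this stands. The LOCF order, the use of baseline and the assignment of in-window exit exams are all unwritten, and the Visit 5 window is printed two ways, though the signs may be a PDF-reading fault. The SAP 6.4 reading is weak: Protocol 8.4.2 separates the Unscheduled Visit pages from the Visit 6/Exit pages and puts early exits on the latter. The risk of a choice made after unmasking is limited because date order is the default that an analyst would need a reason to abandon.

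The harmful examples also draw on a small group. Patients given escape medication stay in the study (Protocol 8.2.2), those who stop drug for other reasons are encouraged to stay (8.6.2), and exits for lack of efficacy are failures wherever the exam is filed. SAP 6.3 plans observed-data and multiple-imputation sensitivity analyses, and the table list adds missing-as-failure (14.2.1.3), so sensitivity to missing-data handling will be visible.

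**Conclusion.** This is a missing derivation detail that analysts would fill sensibly, and no change to the plan follows. Read in the ordinary way, by date and through the visit window, the plan uses every exit exam at issue and the effect is nil. The least favourable date-order reading gives at most 1.4 points per arm for pain and 0.8 for cells, and only on the assumed extremes of four relevant exits per arm, half differing, evenly spread. The larger harm needs a visit-number ordering that the SAP does not state. No change in the trial's conclusion is shown.

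This rests on three assumptions: the exit pages carry the exam date, sites complete the pages of any visit a patient attends, and LOCF is programmed by date. Noting that convention in the programming specification is routine work. The two printings of the Visit 5 window are at most a clerical mismatch and alter no result shown here.
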